9.1.2.1 Assessment and Procedures for Combined Vascular Events

After the occurrence of a combined vascular event, the study center must notify the sponsor within 24 hours upon receipt of the event notice. Vascular events will be reviewed by an independent Clinical Events Committee (CEC). Therefore, the endpoint event classification table will be included as part of the CRF. The investigator will record events in the aforementioned table and promptly submit supporting documents (admission and discharge records, medical records, death records, ECG, etc.). This information will be provided to the CEC for the determination of events.

The CEC is composed of a chairperson and 5–6 members. Each event will be independently reviewed by two members of the committee, and the conclusions will be submitted to the chairperson of the committee. If there is a disagreement between the two reviewing members or between the two reviewing members and the chairperson, when the number of dissenting events reaches a certain threshold, the entire committee will schedule a meeting to review the events.

9.2 Safety determination:

Adverse event assessment

• Clinical laboratory indicators:

Collect blood and urine samples in a fasting state (at least 10 hours of fasting, with water intake allowed but no consumption of coffee or tea) and send them to the laboratories of each center for testing according to uniform standards

Blood routine (hemoglobin, red blood cells, white blood cells, platelets), urine routine (urine protein, urine white blood cells, urine red blood cells), serum biochemistry (alanine aminotransferase, aspartate aminotransferase, alkaline phosphatase, total bilirubin, glutamine, urea nitrogen, creatinine, uric acid, blood glucose, total cholesterol, triglycerides, low-density lipoprotein, high-density lipoprotein), coagulation 4-item

12-lead ECG

Physical examination:

Comprehensive physical examination: General condition (including height, weight), vital signs (including blood pressure, pulse rate), skin (including hair and nails), eyes, ears, nose, and throat, neck/thyroid, chest/lungs, cardiovascular system, abdomen/gastrointestinal system, reproductive-urinary system (optional), nervous system, lymphatic system, and musculoskeletal system;

Simplified physical examination: General condition (including weight), vital signs (including blood pressure, pulse rate), chest/lungs, cardiovascular system

Vital signs: Patient's sitting blood pressure, pulse rate, respiratory rate, and heart rate will be recorded after at least 5 minutes of rest. Blood pressure measurements will be conducted using an appropriately calibrated and validated sphygmomanometer with the auscultatory method. The patient should remain seated for at least 5 minutes, both feet on the ground, and arms at heart level. An appropriately sized cuff should be used (the cuff bladder should encircle at least 80% of the arm) to ensure the accuracy of the measurement. Each blood pressure measurement should be performed twice, with an interval of at least 5 minutes, and the average of the two measurements should be recorded.

10 Observation of Adverse Events

10.1 Definition:

- Adverse event (AEs): Any untoward medical event that occurs from the time the subject signs the *Informed Consent Form* and is enrolled in the study until the last follow-up visit, regardless of whether there is a causal relationship with the study drug.
- Significant adverse event: Any adverse event that, in addition to serious adverse events, leads to the use of targeted medical measures (e.g., drug withdrawal, dose reduction, and symptomatic treatment), and hematological or other laboratory abnormalities.

10.2 Determination criteria for adverse event intensity:

All clinical adverse events occurring in this clinical study will be recorded on the Adverse Events page of the CRF. The intensity of adverse events will be graded. For standardization, the grading of event intensity is as follows:

Mild: Perceptible discomfort, which does not affect daily activities

Moderate: Significant discomfort, affecting or reducing daily activities

Severe: Unable to work or engage in daily activities

The severity and intensity of adverse events should be distinguished. Severe is used to describe intensity, which is not necessarily a serious adverse event (SAE). For example, headache may be severe in intensity but cannot be classified as a SAE unless it meets the SAE criteria.

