6.2 Treatment regimen

6.2.1 Study process:

Screening period (Day -3 to Day 0):

If patients meet the treatment criteria outlined in this protocol, they can undergo all examinations during this period. Patients who meet the inclusion criteria will proceed to the randomization phase.

Random treatment period (Day 1 to Day 90): Designated as Day 1 from the first dose administration.

Treatment group: Standard treatment + Tongxinluo Capsules (4 capsules/time, tid, po)

Control group: Standard treatment + Tongxinluo Capsule Simulant (4 capsules/time, tid, po)

It is recommended to take the study drugs in approximately 30 minutes after daily meals. Patients should not take the drug in the morning of the day of visit at home. If a patient misses a dose on a certain day, the dose the following day should not exceed the daily dose. Dose adjustment of the study drug is not allowed. If a patient develops an intolerable adverse event, which is considered by the investigator to be related to the study drug, he/she should terminate the treatment with the study drug.

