8.1 Visit 1 (V1, Day -3 to Day 0)

(Complete the following tasks within 3 days)

- Sign the *Informed Consent Form*
- Collect general information: gender, age, height, weight, etc.
- Perform brain CT and/or head MRI examination
- Laboratory tests (If the patient has undergone tests during the current hospitalization
 that overlap with the study examination items, there is no need to repeat the tests.
 Instead, the report of these tests should be reprinted or copied and attached to the study
 medical record. The copy must be signed by the investigator.)
- Physical examination
 - 12-lead ECG
 - Pregnancy test

- Assess NIHSS score, mRS score, and BI index score
 - Record concomitant diseases and concomitant medications
- Review inclusion criteria and exclusion criteria
 - Dispense randomized study drugs
- Advise the subjects of the next follow-up date and inform them not to take the drug on the day of the follow-up

Since neuroimaging is routinely recommended for all stroke patients, this study will not cover the cost of this portion during this visit.

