11.4 Randomization

11.4.1 Randomization method

Method of centralized dynamic randomization, with each center competing for enrollment. The centralized randomization procedure will be performed using the Interactive Web-based Randomization System (IWRS) provided by Peking University Clinical Research Institute. The principal investigators at each study center will have their own unique login credentials, ensuring the security and integrity of the login system. After screening each eligible subject at all participating centers in this study, the investigator will log in to the randomization system with their accounts, input relevant information about the subject and obtain the drug packaging number for that subject. The investigators will administer the relevant drug based on the drug

packaging number. Subjects will be randomized into treatment and control groups based on stratification factors, which include:

- 1. Whether thrombolytic therapy has been administered: Yes, No
- 2. NIHSS Score: 4–7 points, 8–14 points, 15–22 points

The randomization method is the Pocock and Simon minimization algorithm. Patients must initiate the study treatment within 24–48 hours after randomization. This study employs non-repeated randomization.

12 Statistical Analysis

After the study protocol is finalized, statistical professionals will collaborate with the principal investigator to develop the statistical analysis plan. The statistical analysis software used is SAS® 9.2 software (Software installation point authorization code: 11202165). The sample size calculation software used is PASS 11.

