4.2 Randomization and implementation

All patients are randomly divided into the treatment group and control group at a ratio of 1:1. Central dynamic randomization is adopted so that each center is grouped in competition. The centralized random grouping program will be performed with Interactive Web-based Randomization System (IWRS) provided by the Peking University Clinical Research Institute. The main investigators have their own accession numbers and passwords to

ensure the security and integrity of the login system. After screening each eligible participant in each study center, the researchers should enter the randomized system with the account number and enter the information about the subject to obtain related drug package number. The researchers should deliver drugs according to the drug package number. Subjects are randomly assigned to the treatment and control groups according to stratification factors, and stratification factors include:

- 1. Has take thrombolytic therapy: Yes or no
- 2. NIHSS score: 4-7 points, 8-14 points and 15-22 points;

The randomization method is Pocock and Simon minimal randomization. Patients must start treatment within 24-48 hours after randomization. This study is treated with non-repetitive randomization.

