6.1.3 Safety set (SS)

Safety set (SS): The actual data that patients accept at least one time treatment with safety indexes recording. Do not do data-carry-forward if safety is missing; the incidence of adverse events takes the number of safety set as denominator.

SS population is the main population for safety evaluation in this study.

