6.2.5 Safety analysis

Adverse events are described with case number, times and incidence of various adverse events, and $\chi 2$ test or Fisher's exact test is adopted for comparing the incidence between the two groups. At the same time, make a detailed list to describe the specific manifestation and extent of all adverse events and serious adverse events and their relation with drugs.

Statistically describe the vital signs at baseline and 90 days after treatment according to general principles, and make comparison between former and later times and inter-group comparison.

Make description of number of normal cases before treatment, number abnormal cases after treatment and their ratios in two groups, respectively, and $\chi 2$ test or Fisher's exact test is adopted for comparing the ratio between the two groups.

Make description of number of normal cases before treatment, number abnormal cases after treatment and their ratios in two groups, respectively, and $\chi 2$ test or Fisher's exact test is adopted for comparing the ratio between the two groups. Crosstab is adopted to describe the change of laboratory indexes before and after treatment for determining the clinical significance of these indexes.

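### The all-AE and SAE comparisons have no first-dose cut-off, so events before dosing are counted and slightly attenuate any true difference between arms

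*Combined protocol and SAP*

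**What the plan says.** **When events start to count.** The adverse-event definition in protocol 10.1 opens with "Any untoward medical event that occurs from the time the subject signs the" (the consent form is meant). Enrolment is a second condition, counting ends with the final visit, and causality plays no part.

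**When treatment starts.** Protocol 11.4.1: "Patients must initiate the study treatment within 24–48 hours after randomization". SAP 4.2 says the same: "Patients must start treatment within 24-48 hours after randomization". Protocol 6.2.1 anchors the treatment period on the first dose: "Designated as Day 1 from the first dose administration".

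**Who is counted.** In protocol 12.1 the safety set is the randomized patients who took study drug and had a safety assessment after baseline. SAP 6.1.3 likewise requires at least one treatment and adds that "the incidence of adverse events takes the number of safety set as denominator". Both rules select patients. Neither selects events by onset.

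**What is compared.** SAP 6.2.5: "Adverse events are described with case number, times and incidence of various adverse events", with a chi-square or Fisher test between groups. Table 7.4.1.1 has a P-value column and rows for all adverse events, serious events, severe events, events causing drop-out, and drug-related events (overall and severe). No section defines a treatment-emergent event.

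**The concern.** An event that begins after enrolment but before the first capsule cannot be an effect of the capsule. Under the rules above it is still counted, under the assigned arm, for any patient who later takes a dose and enters the safety set. Such events add a similar amount to both arms. That pulls the risk ratio towards 1 and adds noise to the comparison meant to reveal an excess of harm.

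The rest of SAP 6.2.5 is anchored on treatment: laboratory and examination findings are counted when normal before treatment and abnormal after it. Only the adverse-event counts lack that anchor. What is at stake is some sensitivity of the all-AE and SAE rows.

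**Working it through.** **The plan's own figure.** The only design calculation is for the primary endpoint (protocol 4.2, SAP 4.4): 40% vs 47%, two-sided 0.05, 80% power.

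n = [1.960·√(2·0.435·0.565) + 0.842·√(0.40·0.60 + 0.47·0.53)]² / 0.07² = 787 after rounding up. Then 787/0.80 = 984 per arm, 1,968 in total. This reproduces. The documents give no AE rate, no AE timing and no power for safety, so everything below rests on assumed rates.

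**Length of the gap.** Take the longest post-randomization gap, 48 hours, followed by 90 days of treatment.

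**Share of events before dosing (s).**
- Constant event rate: 2/92 = 2.2%.
- Early clustering, modelled as cumulative events proportional to time^k over about 95 days, with the clock starting when counting starts: (2/95)^0.6 = 9.9% and (2/95)^0.5 = 14.5%.
- Same shapes, but with the clock starting at stroke onset and randomization d = 0.5 to 3 days later: s = [(d+2)^k − d^k]/[(d+92)^k − d^k]. This gives 7.4% down to 5.2% for k = 0.6, and 9.8% down to 6.3% for k = 0.5.

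The table therefore uses 2.2%, 5%, 10% and 15%.

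**Conversion to patients.** The planned tests compare patients with an event. With p the control arm's on-treatment incidence, the pre-dose incidence in either arm is q = s·p/(1−s). The observed incidence in an arm is q + (1−q)·(on-treatment incidence). This treats pre-dose and on-treatment events as independent.

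Example, 10% vs 14% at s = 2.2%: q = 0.0217·0.10/0.9783 = 0.0022. Observed control is 0.0022 + 0.9978·0.10 = 0.1020, and observed treatment is 0.0022 + 0.9978·0.14 = 0.1419. The risk difference is 3.99 points instead of 4.00, and the risk ratio is 1.39 instead of 1.40.

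**Power at 984 per arm, two-sided 0.05:**

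| On-treatment rates | s = 0 | 2.2% | 5% | 10% | 15% |
|---|---|---|---|---|---|
| 10% vs 14% | 78.0% | 77.2% | 76.2% | 74.3% | 72.2% |
| 20% vs 26% | 88.6% | 88.0% | 87.2% | 85.5% | 83.6% |
| 5% vs 7.5% | 63.0% | 62.2% | 61.2% | 59.3% | 57.3% |

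The loss is 0.6 to 0.8 points at a constant rate and 1.4 to 5.8 points across the early-clustering shares. At s = 15% the risk differences are 3.93, 5.79 and 2.48 points against true values of 4.00, 6.00 and 2.50. The risk ratios fall from 1.40, 1.30 and 1.50 to 1.34, 1.25 and 1.42.

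**The case against.** The strongest reply is that this is a small drafting gap with safeguards already around it.

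- The drug-related rows of Table 7.4.1.1 are largely protected, because the first causality criterion in protocol 10.3 is the timing of onset relative to starting the drug. This stands. However, it depends on investigator judgement and does not clean the all-AE or SAE rows.
- Ischemic stroke, TIA and myocardial infarction are kept out of AE/SAE by protocol 10.4.2, which removes some early events. This stands. All deaths and any hemorrhagic event remain in.
- Collecting events from consent is not an error. This stands: the gap is in the analysis window.

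Some stronger readings are tempting, but the documents do not support them.

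- *A five-day pre-dose window* (three days of screening plus 48 hours). The definition requires enrolment as well as consent. The visit schedules first record adverse events at Visit 2. With inclusion limited to 72 hours from onset, three full days of screening would need consent at about the moment of onset.
- *The pre-dose days are the most eventful.* The guideline in Appendix 7 places the acute phase at roughly the first two weeks and calls urinary dysfunction common early. That is qualitative support for clustering, but it gives no daily event rates.
- *Table 7.4.1.1 offers only one overall comparison.* It has several rows, including the drug-related ones.
- *Much larger power losses.* These appear if q is set directly at, say, 5%. With a 5% on-treatment rate, that means 0.05/(0.05 + 0.95·0.05) = 51% of affected control patients had a pre-dose event. Nothing in the documents suggests this.

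**Conclusion.** The point holds as a minor, inexpensive improvement. As written, events between enrolment and first dose in patients later dosed are counted in the tested all-AE and SAE rows, and no section removes them. A reader might infer a bias that hides harm in one arm's favour. Randomization does not allow that reading: pre-dose events are balanced in expectation, and the effect is attenuation only.

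The size is about 1 point of power at a constant event rate and roughly 2 to 6 points if events cluster early, with almost no change in the risk difference. These figures rest on assumed AE rates, an assumed clustering shape, the full 48-hour gap for every patient, and all 984 patients per arm being in the safety set. A shorter gap would reduce the loss.

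**What to change.** Keep collecting from consent and enrolment. In SAP 6.2.5, define a treatment-emergent event as one that starts, or worsens, on or after the first dose. Base the between-group AE and SAE tests in Table 7.4.1.1 on those events, with the safety set as denominator, and list earlier events separately by arm.

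The cost is a short SAP amendment and minor programming. Before relying on it, confirm that the CRF captures the date and time of first dose and of AE onset, because same-day events need times. Protocol 10.6.1 asks for onset time of adverse drug reactions in the medical records, which does not show that either item is a CRF field. The 24–48 hour wording in protocol 11.4.1 and SAP 4.2 can be read as a range or as a maximum and should be clarified, since it sets the length of the gap. Clinical care and event reporting do not change.

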10.3 Criteria for determining the relationship between adverse events and study drug

For causal analysis of all adverse events with the study drug, assessments will be made using five levels: definitely related, probably related, possibly related, unlikely related, and definitely unrelated. The first three are categorized as adverse drug reactions. The considerations for causal analysis include the following five aspects:

- 1) Whether there is a reasonable temporal relationship between the initiation of drug use and the onset of suspected Adverse Drug Reactions (ADR).
- 2) Whether the suspected ADR aligns with the known ADR of the drug (as per the literature).
- 3) Whether the suspected ADR can be explained by concurrent medication, previous medication, the patient's clinical condition, or the influence of other therapies (other

Page 22 of 76

explanations).

4) Whether the suspected ADR resolves or diminishes after discontinuation or dose reduction of the drug (withdrawal response).

5) Whether the suspected ADR reappears upon re-exposure to the same drug (rechallenge).

10.4 Determination of serious adverse events

10.4.1 Definition of common serious adverse events

A serious adverse event refers to any clinical event that suggests significant harm, contraindications, side effects, or requires caution. An adverse event is classified as a serious adverse event if it meets one or more of the following criteria:

Death

• Life-threatening (referring to instances where patients experiencing the event are at an immediate risk of death at the time of occurrence; excludes events that, if more severe, could potentially lead to patient death)

• Leading to hospitalization or prolonged hospital stay

• Results in persistent or significant labor loss or disability

• Congenital malformation or defect

Some medical events that have not resulted in death, are not life-threatening, or do not require hospitalization, but, in the investigator's medical judgment, may jeopardize the patient's well-being or require medical or surgical intervention to prevent one of the outcomes listed above, should also be considered as an SAE.

10.4.2 Study-specific definition of serious adverse events

The following events are recorded only as endpoint events and are not considered as AE/SAE

1. Ischemic stroke

2. TIA

3. Myocardial infarction

The following events are considered both endpoint events and AE/SAE

1. Hemorrhagic stroke

2. Vascular death

All deaths and any hemorrhagic events should be reported as AE/SAE

10.5 Operational procedures

- (1) In the process of drug clinical study, personnel at all positions have their own responsibilities and duties, and perform their tasks in accordance with the regulations.
- (2) Strictly adhere to the standard operating procedures at each stage of the drug clinical study.
- (3) During the drug clinical study, study staff should closely observe or follow up on various reactions occurring in subjects after drug administration, in order to promptly detect adverse events or serious adverse events and provide timely intervention.
- (4) During the drug clinical study, once a subject experiences an adverse reaction, regardless of its causal relationship with the study drug, the investigator should record all adverse events in the original records and sign them. If it is an adverse drug reaction, a preliminary assessment and diagnosis or suspected diagnosis of the adverse reaction should be made based on the criteria for determining the causality between adverse drug reactions and the drug.
- (5) For subjects experiencing common adverse reactions to the study drug, the investigator should immediately report to the PI, determine necessary diagnostic and treatment measures based on the condition, decide whether to discontinue the clinical study, follow up and investigate all adverse events, record the detailed process and outcomes until the issue is resolved or the condition stabilizes. If there are laboratory abnormalities, follow-up should continue until recovery to normal. The follow-up method can be chosen based on the severity of the adverse reactions, including options such as hospitalization, outpatient visits, home visits, phone calls, and communication.
- (6) In the case of serious adverse events, the doctor should immediately initiate rescue according to the Emergency Response SOP and record it. Consultation with relevant specialized departments should be requested, and in cases of urgency, the subject should be urgently transported to the ICU for treatment, accompanied by medical staff. In addition, the PI should be immediately notified, and the Subject Injury and Adverse Event Handling Team should be promptly informed. During holidays, hospital on-call personnel should be notified, and reporting should be escalated as appropriate. The emergency response flowchart can be found in Appendix 5.

(7) Report and unblind according to the "Standard Operating Procedure for Reporting Serious Adverse Events" (see 10.6.3.1) and the "Standard Operating Procedure for Emergency Unblinding" (see 11.2).

